8 LIST OF TABLES

Table 1 Demographic Characteristics – All Subjects

Table 1.1 Demographic Characteristics by line of treatment (1st line vs. 2nd and later line) – All Subjects

Table 2 Initial and Advance Breast Cancer Diagnosis – All Subjects

Table 2.1 Initial and Advance Breast Cancer Diagnosis by line of treatment (1st line vs. 2nd and later line) – All Subjects

Table 3 Advance Breast Cancer Diagnosis – All Subjects

Table 3.1 Advance Breast Cancer Diagnosis by line of treatment (1st line vs. 2nd and later line) – All Subjects

Table 4 Prior Therapy – All Subjects

Table 4.1 Prior Therapy by line of treatment (1st line vs. 2nd and later line) – All Subjects

Table 5 Performance Status – All Subjects

Table 5.1 Performance Status by line of treatment (1st line vs. 2nd and later line) – All Subjects

Table 6 Early Breast Cancer Treatment History – All Subjects

Table 6.1 Early Breast Cancer Treatment History by line of treatment (1st line vs. 2nd and later line) – All Subjects

Table 7 Palbociclib Treatment – All Subjects

Table 7.1 Palbociclib Treatment by line of treatment (1st line vs. 2nd and later line) – All Subjects

Table 8 Dose Adjustment – All Subjects

Table 8.1 Dose Adjustment by line of treatment (1st line vs. 2nd and later line) – All Subjects

Table 9 Palbociclib Treatment- Supportive Therapies – All Subjects

Table 9.1 Palbociclib Treatment- Supportive Therapies by line of treatment (1st line vs. 2nd and later line) – All Subjects

Table 10 Advance Breast Cancer Treatment History – All Subjects

Table 10.1 Advance Breast Cancer Treatment History by line of treatment (1st line vs. 2nd and later line) – All Subjects

Table 11 Clinical Outcome – All Subjects

Table 11.1 Clinical Outcome by line of treatment (1st line vs. 2nd and later line) – All Subjects

10 APPENDICES

10.1 APPENDIX 1: MOCK SHELLS FOR TABLES

Table 1 Demographic Characteristics – All Subjects

Characteristic (Unit)	Statistics	Palbociclib (N=xx)
Age of the patients	n	xx
	Mean (SD)	xx.x (xx.xx)
	Median	xx.x
	Min, Max	xx, xx
Age group >65 yrs vs <65 yrs	n (%)	
Menopause Status		
Induced	n (%)	xx (xx.x)
Natural	n (%)	xx (xx.x)
Type of Induced Menopause		
LHRH suppression	n (%)	xx (xx.x)
Radioablation	n (%)	xx (xx.x)
Surgical	n (%)	xx (xx.x)
Patient deceased		
No	n (%)	xx (xx.x)
Yes	n (%)	xx (xx.x)
Family History of Breast Cancer		
No	n (%)	xx (xx.x)
Yes	n (%)	xx (xx.x)
Abbreviations: N = number of subjects in Palbociclib group; n = number of subjects in specified category; LHRH = Luteinizing Hormone Releasing Hormone		
Note 1: Percentages are based on the number of subjects in the Palbociclib group.		
Table 1.1 Demographic Characteristics by line of treatment (first line vs. second and later line)		

PFIZER CONFIDENTIAL

Table 2 Initial and Advance Breast Cancer Diagnosis– All Subjects

Characteristic (Unit)	Statistics	Palbociclib (N=xx)
Stage of Breast Cancer at diagnosis		
Stage I	n (%)	xx (xx.x)
Stage II	n (%)	xx (xx.x)
Stage IIIa	n (%)	xx (xx.x)
Stage IIIb	n (%)	xx (xx.x)
Stage IIIc	n (%)	xx (xx.x)
Stage IV	n (%)	xx (xx.x)
Type of breast cancer (Metastatic/ locally advanced)		
Locoregionally advanced	n (%)	xx (xx.x)
Metastatic	n (%)	xx (xx.x)
Abbreviations: N = number of subjects in Palbociclib group; n = number of subjects in specified category		
Note 1: Percentages are based on the number of subjects in the Palbociclib group.		
Table 2.1 Initial and Advance Breast Cancer Diagnosis by line of treatment (first line vs. second and later line)		

Table 3 Advance Breast Cancer Diagnosis – All Subjects

PFIZER CONFIDENTIAL

Characteristic (Unit)	Statistics	Palbociclib (N=xx)
Sites of Metastases		
Bone	n (%)	xx (xx.x)
Lung	n (%)	xx (xx.x)
Liver	n (%)	xx (xx.x)
Lymph nodes	n (%)	xx (xx.x)
-----	-----	-----
-----	-----	-----
Bone		
Single site	n (%)	xx (xx.x)
Multiple sites	n (%)	xx (xx.x)
Liver		
Single site	n (%)	xx (xx.x)
Multiple sites	n (%)	xx (xx.x)
Lung		
Single lung	n (%)	xx (xx.x)
Bilateral	n (%)	xx (xx.x)
Pleural effusion	n (%)	xx (xx.x)
Lymph Nodes		
Regional	n (%)	xx (xx.x)
Distal	n (%)	xx (xx.x)

Abbreviations: N = number of subjects in Palbociclib group; n = number of subjects in specified category

Note 1: Percentages are based on the number of subjects in the Palbociclib group.

Table 3.1 Advance Breast Cancer Diagnosis by line of treatment (first line vs. second and later line)

Table 4 Prior Therapy– All Subjects

PFIZER CONFIDENTIAL

Characteristic (Unit)	Statistics	Palbociclib (N=xx)
Prior Therapy		
Targeted	n (%)	xx (xx.x)
Endocrine	n (%)	xx (xx.x)
Chemotherapy	n (%)	xx (xx.x)
Abbreviations: N = number of subjects in Palbociclib group; n = number of subjects in specified category		
Note 1: Percentages are based on the number of subjects in the Palbociclib group.		
Table 4.1 Prior Therapy by line of treatment (first line vs. second and later line)		

Table 5 Performance Status– All Subjects

PFIZER CONFIDENTIAL

Characteristic (Unit)	Statistics	Palbociclib (N=xx)
Performance Status on ECOG Scale at Palbociclib initiation		
0	n (%)	xx (xx.x)
1	n (%)	xx (xx.x)
2	n (%)	xx (xx.x)
3	n (%)	xx (xx.x)
4	n (%)	xx (xx.x)
5	n (%)	xx (xx.x)
Abbreviations: N = number of subjects in Palbociclib group; n = number of subjects in specified category; ECOG = Eastern Cooperative Oncology Group		
Note 1: Percentages are based on the number of subjects in the Palbociclib group.		
Table 5.1 Performance Status by line of treatment (first line vs. second and later line)		

PFIZER CONFIDENTIAL

Table 6 Early Breast Cancer Treatment History – All Subjects

Characteristic (Unit)	Statistics	Palbociclib (N=xx)
Neo/Adjuvant Therapy Received by Patient		
Adjuvant chemotherapy	n (%)	xx (xx.x)
Adjuvant endocrine therapy	n (%)	xx (xx.x)
Neoadjuvant treatment	n (%)	xx (xx.x)
Radiotherapy	n (%)	xx (xx.x)
Surgery	n (%)	xx (xx.x)
Don't Know	n (%)	xx (xx.x)
Abbreviations: N = number of subjects in Palbociclib group; n = number of subjects in specified category		
Note 1: Percentages are based on the number of subjects in the Palbociclib group.		
Table 6.1 Early Breast Cancer Treatment History by line of treatment (first line vs. second and later line)		

PFIZER CONFIDENTIAL

Table 7 Palbociclib Treatment – All Subjects

Characteristic (Unit)	Statistics	Palbociclib (N=xx)
Initial Dose Prescribed		
125 mg/day	n (%)	xx (xx.x)
100 mg/day	n (%)	xx (xx.x)
75 mg/day	n (%)	xx (xx.x)
Dose Adjustment		
No	n (%)	xx (xx.x)
Yes	n (%)	xx (xx.x)
Reason for Dose Adjustment		
Side effects/toxicity	n (%)	xx (xx.x)
Lack of response	n (%)	xx (xx.x)
Patient request	n (%)	xx (xx.x)
Other reasons	n (%)	xx (xx.x)
Abbreviations: N = number of subjects in Palbociclib group; n = number of subjects in specified category		
Note 1: Percentages are based on the number of subjects in the Palbociclib group.		
Table 7.1 Palbociclib Treatment by line of treatment (first line vs. second and later line)		

PFIZER CONFIDENTIAL

Table 8 Dose Adjustment – All Subjects

Characteristic (Unit)	Statistics	Palbociclib (N=xx)
Dose Reduced		
Yes	n (%)	xx (xx.x)
Dose Resumed following interruption or cycle delay		
Yes	n (%)	xx (xx.x)
Dose Interrupted (temporarily stopped during a dose cycle)		
Yes	n (%)	xx (xx.x)
Cycle delay (the next cycle is pushed back)		
Yes	n (%)	xx (xx.x)
Combination partner therapy continued		
Yes	n (%)	xx (xx.x)
Abbreviations: N = number of subjects in Palbociclib group; n = number of subjects in specified category		
Note 1: Percentages are based on the number of subjects in the Palbociclib group.		
Table 8.1 Dose Adjustment by line of treatment (first line vs. second and later line)		

PFIZER CONFIDENTIAL

Table 9 Palbociclib Treatment- Supportive Therapies – All Subjects

Characteristic (Unit)	Statistics	Palbociclib (N=xx)
Supportive therapies		
Nutritional Support	n (%)	xx (xx.x)
Bisphosphonates	n (%)	xx (xx.x)
Antibiotics	n (%)	xx (xx.x)
Anti-anxiety drugs	n (%)	xx (xx.x)
Opioid extended release	n (%)	xx (xx.x)
NSAIDs	n (%)	xx (xx.x)
-----	-----	-----
-----	-----	-----
-----	-----	-----
Don't Know	n (%)	xx (xx.x)
Abbreviations: N = number of subjects in Palbociclib group; n = number of subjects in specified category		
Note 1: Percentages are based on the number of subjects in the Palbociclib group.		
Table 9.1 Palbociclib Treatment- Supportive Therapies by line of treatment (first line vs. second and later line)		

PFIZER CONFIDENTIAL

Table 10 Advance Breast Cancer Treatment History – All Subjects

Characteristic (Unit)	Statistics	Palbociclib (N=xx)
Time duration from Diagnosis to initiation of Palbociclib	n	xx
	Mean (SD)	xx.x (xx.xx)
	Median	xx.x
	Min, Max	xx, xx
Line of treatment		
1st line	n (%)	xx (xx.x)
2nd line	n (%)	xx (xx.x)
3rd line	n (%)	xx (xx.x)
4th or later line	n (%)	xx (xx.x)
Abbreviations: N = number of subjects in Palbociclib group; n = number of subjects in specified category		
Note 1: Percentages are based on the number of subjects in the Palbociclib group.		
Table 10.1 Advance Breast Cancer Treatment History by line of treatment (first line vs. second and later line)		

PFIZER CONFIDENTIAL

Table 11 Clinical Outcome – All Subjects

Characteristic (Unit)	Statistics	Palbociclib (N=xx)
Complete response		
Yes	n (%)	xx (xx.x)
Partial response		
Yes	n (%)	xx (xx.x)
Stable disease		
Yes	n (%)	xx (xx.x)
Progressive disease		
Yes	n (%)	xx (xx.x)
Objective Response Rate (ORR)		
Yes	n (%)	xx (xx.x)
Clinical Benefit Rate (CBR)		
Yes	n (%)	xx (xx.x)

CCI

Abbreviations: N = number of subjects in Palbociclib group; n = number of subjects in specified category

[figure not shown]
Note 1: Percentages are based on the number of subjects in the Palbociclib group.

PFIZER CONFIDENTIAL

Table 11.1 Clinical Outcome by line of treatment (first line vs. second and later line)

A large black rectangular redaction box covers the majority of the page content below the table caption. Within this redaction, the letters 'CCI' are printed in large, bold, red font, likely representing the first few letters of the table title.

CCI

A horizontal black redaction bar is located at the bottom of the page, obscuring the bottom portion of the page content.

PFIZER CONFIDENTIAL

PFIZER CONFIDENTIAL

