2.1 STUDY DESIGN

This is a post marketing, retrospective, non-interventional study (NIS). The study will be conducted as a retrospective medical record review of patients who have received palbociclib combination with aromatase inhibitor (as prescribed by the Physician) in menopausal state as initial endocrine therapy in MBC or with fulvestrant after progression on prior endocrine therapy. It will comprise of an initial screening and eligibility assessment of patients followed by data collection from eligible patient records.

Data collection will be conducted using a predesigned electronic case report form (eCRF). Eligible physicians will be invited to complete the eCRF of patients that meet the study criteria. Patient eligibility will be confirmed by treating physicians. In order to allow for a sufficiently long observational window, treating physicians will be asked to go back to a specific point in time, the index date, and sequentially select the medical records of the next 'n' patients who meet the inclusion criteria.

Study population

Female cancer patients who have received palbociclib combination treatments for HR+/HER2- ABC/MBC in real world clinical practice setting.

Data source

Data will be collected from the Indian routine clinical practice settings. Approximately 10 oncologists will be included based on predefined egilbility criteria. Each selected physician will complete at least 10-15 electronic case report forms (eCRFs).

PFIZER CONFIDENTIAL

To be eligible, physicians must have treated or be treating 10 or more HR+/HER2-ABC/MBC patients who meet the eligibility criteria for the study. This will ensure that recruited physicians will be able to complete the minimum number of eCRFs required to participate in the study. In addition, during physician recruitment a representative geographical split and private/public practice split will be sought where possible to ensure a representative sample.

Inclusion Criteria

Physician inclusion criteria

- Oncologist.
- Responsible for treating ≥ 10 ABC/MBC patients who meet the eligibility criteria.
- Agrees to participate in the study and complete the eCRFs within the data collection period

Patients Inclusion Criteria

Patients must meet all of the following inclusion criteria to be eligible for inclusion in the study:

- ≥ 18 years old females.
- HR+/HER2- breast cancer diagnosis with confirmed metastatic or advanced disease.

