2.2 STUDY OBJECTIVES

Primary Objectives:

1. To describe the demographics and clinical characteristics of patients who have received palbociclib combination with aromatase inhibitor (as prescribed by the Physician) in menopausal state as initial endocrine therapy in MBC or with fulvestrant after progression on prior endocrine therapy.
2. To summarize adjuvant therapies received for the treatment of early or locally advanced breast cancer (Stages 0-IIIa).
3. To describe treatments received in the advanced/metastatic setting, before and after palbociclib combination use.
4. To describe dosing and dose changes, interruptions, delays, and discontinuations associated with palbociclib use in clinical practice.
5. To describe supportive therapies received by patients while receiving palbociclib combination treatments.
6. To determine in overall population and defined subgroups, clinical outcomes including (but not limited to):
 - Proportion of patients who are progression free at specific intervals (eg, 6, 12, 18 months).
 - Objective response rate (ORR) - depending on availability of follow-up data.
 - Proportion of alive patients 1 and 2 years post palbociclib combination initiation -depending on availability of follow-up data (sample size permitting).

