7.2 STATISTICAL ANALYSES

- **Demographic Characteristics**

The demographic and baseline characteristics will be summarized by using descriptive statistics. Continuous variables such as age will be summarized by number of observations (n), arithmetic mean (mean), standard deviation (SD), median, minimum value (min), and maximum value (max) and Categorical variables such as menopausal status, induced menopause, family history of breast cancer and patient deceased will be presented by frequency (n) and percentage (%).

- **Initial and advance breast cancer diagnosis**

For all the patients initial diagnosis of breast cancer stages (stage 0 to stage IV) will be presented in frequency counts (n) and percentage (%). For the advance stages (stage IIIb, IIIc or IV) of breast cancer patients again locoregionally advanced or metastatic frequency counts (n) and percentage (%) will be given. For the metastatic disease, sites of metastases such as Bone, Liver, Brain, Lung, Lymph nodes and others with further segregation like single or multiple locations will be presented in frequency (n) and percentage (%).

- **Prior Therapy**

For all patient's prior therapy type (Targeted, Endocrine and Chemotherapy) will be presented by frequency count and percentage

- **Performance status**

Performance status using ECOG scale at the initiation of palbociclib treatment. Status is measured using 4 point scale from fully active to completely disable and will be summarized by frequency (n) and percentage (%).

- **Early Breast Cancer Treatment History**

Following early breast cancer diagnosis treatments received such as surgery, radiotherapy, neoadjuvant treatment, adjuvant chemotherapy, adjuvant endocrine therapy by patients will be summarized by frequency (n) and percentage (%).

- **Palbociclib Treatment**

PFIZER CONFIDENTIAL

For all the patients initial dose prescribed of palbociclib, any dose adjustments made to palbociclib and for each dose adjustment if dose reduced or increased, palbociclib was temporarily interrupted, cycle delay and reason for dose change will be summarized by frequency (n) and percentage (%). Moreover, complete summary (frequency and percentage) of all supportive therapies that patients received will be presented.

- **Advance Breast Cancer Treatment History**

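### Age exactly 65 falls in neither age group in the SAP Table 1 shell, and the shells omit the Stage 0 and dose-increase rows that SAP 7.2 calls for

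*SAP*

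**What the plan says.** **Age.** The Table 1 shell (SAP Appendix 1) carries one age-group label, "Age group >65 yrs vs <65 yrs", with no separate rows beneath it. Eligibility is "≥ 18 years old females" with no upper limit (SAP 2.1), so 65 is an eligible age. Protocol 9.3 lists age as a variable but gives no cut-point.

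**Stage.** SAP 7.2 commits to the full range: "initial diagnosis of breast cancer stages (stage 0 to stage IV) will be presented in frequency counts (n) and percentage". In the Table 2 shell, the block headed "Stage of Breast Cancer at diagnosis" has rows for I, II, IIIa, IIIb, IIIc and IV only.

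**Dose changes.** SAP 7.2 lists what will be summarised: "for each dose adjustment if dose reduced or increased, palbociclib was temporarily interrupted, cycle delay and reason for dose change". The Table 8 shell has rows for reduction, resumption, interruption, cycle delay and continuation of the partner therapy. Table 7 has a yes/no row for any dose adjustment and a list of reasons, but no direction of change.

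**Denominator.** Note 1 under each of these tables bases percentages on all subjects in the Palbociclib group. SAP 7.1 asks for a missing category where data are not available. SAP 4.1 gives the set as 150 patients.

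**The concern.** A shell is what the programmer builds from. Followed literally, the age rule leaves out one eligible year of age, and the two group percentages need not total 100 even when every age is known. The missing category in SAP 7.1 does not help, because a 65-year-old has a recorded age. A reader could take the shortfall for missing data, or a programmer could settle the matter after seeing the data.

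For stage and dose changes the difficulty is that two parts of the same plan disagree. Stage at diagnosis is a clinical characteristic under objective 1. Dose increases are among the dose changes that objective 4 sets out to describe. If the shells prevail over the text, Stage 0 patients have no row in Table 2, and an increase cannot be told apart from any other adjustment. The same gaps would carry into Tables 1.1, 2.1 and 8.1.

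**Working it through.** The plan states no figure on this point to reproduce. The check compares categories, followed by an illustration of size.

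**Step 1: categories against rows.**

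| Item | Required or possible | Provided in the shell | Left over |
|---|---|---|---|
| Age (Table 1) | every whole year from 18 up | above 65; below 65 | 65 |
| Stage (Table 2) | 0, I, II, IIIa, IIIb, IIIc, IV | I, II, IIIa, IIIb, IIIc, IV | 0 |
| Dose change (Table 8) | reduced, increased, interrupted, cycle delay | reduced, resumed, interrupted, cycle delay, partner continued | increased |

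Testing each integer age from 18 to 99 against the two strict bounds leaves 65 and no other. Resumption after an interruption or delay is not an increase, so that row does not fill the gap in Table 8.

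**Step 2: could the gaps be redactions or open lists?** The shells of Tables 1, 2 and 8 show no redaction mark. Tables 3 and 9 use dashed placeholder rows to signal further categories. Tables 2 and 8 do not.

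**Step 3: how many patients are aged 65?** This needs an assumption, since no age distribution is given. Take age as normal with mean m and SD s, and count as 65 anyone from the 65th birthday up to the 66th:

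p = Φ((66 − m)/s) − Φ((65 − m)/s); expected number = 150 × p; chance of at least one = 1 − (1 − p)^150.

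| m | s | p | 150 × p | chance of at least one |
|---|---|---|---|---|
| 50 | 8 | 0.0076 | 1.1 | 0.684 |
| 50 | 12 | 0.0144 | 2.2 | 0.887 |
| 55 | 10 | 0.0230 | 3.4 | 0.969 |
| 60 | 10 | 0.0343 | 5.1 | 0.995 |
| 65 | 8 | 0.0497 | 7.5 | 1.000 |
| 65 | 12 | 0.0332 | 5.0 | 0.994 |

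Across mean 50 to 65 and SD 8 to 12, p runs from 0.8% to 5.0%. With all subjects as denominator, the two age-group percentages would fall short of 100 by that much.

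**Step 4: Stage 0 and dose increases.** The documents give nothing from which to estimate either count, so none is offered.

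**Step 5: after the change.** With one age bound inclusive and the two rows added, nothing is left over in any line of the first table.

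**The case against.** The strongest reply is that the SAP's text already governs. SAP 7.1 says that categorical variables are summarised over every value they can take, and 7.2 names Stage 0 and dose increases outright. The tables are mock shells, and a careful programmer would add both rows. This largely stands. These two items are conflicts between text and shell, not a decision to omit patients. It does not settle age 65, which the text never places.

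The age label may also be shorthand: it is a single line with an empty result cell, and an underline beneath one of the signs could have been lost when the PDF was read. This cannot be ruled out. A true ≥ sign does survive elsewhere in the SAP, so the label is taken as it stands.

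A reader might infer more than the documents support:

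- **That these patients are dropped from the analysis.** They are not. A 65-year-old stays in N and in the mean, SD, median and range of age in Table 1. A patient whose dose was increased counts as having an adjustment, with a reason, in Table 7. Only the direction is lost.
- **That the loss would be hidden.** For age and stage, percentages adding to less than 100 would show it. It could be confused with missing data only if the missing category from SAP 7.1 were also left out.
- **That Table 8 should add up.** Its rows are overlapping yes items and were never meant to sum to N.
- **That objective 2 is affected.** That objective is "To summarize adjuvant therapies received for the treatment of early or locally advanced breast cancer (Stages 0-IIIa"), and it is reported in Table 6, which has no stage rows and leaves out no Stage 0 patient.

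**Conclusion.** The point holds as a minor reporting correction under objectives 1 and 4. The age split is wrong as written: it misses one eligible year, and no visible text repairs it. Its size is about 1 to 7.5 of 150 patients, assuming normally distributed age with mean 50 to 65 and SD 8 to 12. The true figure depends on an age distribution that the documents do not give. The missing Stage 0 and dose-increase rows are inconsistencies between the shells and SAP 7.2, which 7.1 and 7.2 partly resolve. Their counts are unknown. Response, progression-free and survival results do not change, nor does the study size. No dose or clinical rule is judged here.

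**What to change.** - **Tables 1 and 1.1:** replace the age label with two rows, one of them inclusive, for example <65 years and ≥65 years.
- **Tables 2 and 2.1:** add a Stage 0 row.
- **Tables 8 and 8.1:** add a row for dose increased.
- **Programming check:** for mutually exclusive variables such as age group and stage, require the categories plus the missing category already provided in SAP 7.1 to sum to N. Do not apply this check to Table 8.

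The cost is three shell edits carried to the by-line versions, made before the tables are programmed. The Stage 0 and dose-increase rows only deliver what SAP 7.2 already promises. No new analysis is added.

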### Primary objectives

- To describe the demographics and clinical characteristics of patients who have received palbociclib combination with aromatase inhibitor (as prescribed by the Physician) in menopausal state as initial endocrine therapy in MBC or with fulvestrant after progression on prior endocrine therapy.
- To summarize adjuvant therapies received for the treatment of early or locally advanced breast cancer (Stages 0-IIIa).
- To describe treatments received in the advanced/metastatic setting, before and after palbociclib combination use.
- To describe dosing and dose changes, interruptions, delays, and discontinuations associated with palbociclib use in clinical practice.
- To describe supportive therapies received by patients while receiving palbociclib combination treatments.
- To determine in overall population and defined subgroups, clinical outcomes including (but not limited to):
  - Proportion of patients who are progression free at specific intervals (eg, 6, 12, 18 months).
  - Objective response rate (ORR) - depending on availability of follow-up data.
  - Proportion of alive patients 1 and 2 years post palbociclib combination initiation - depending on availability of follow-up data (sample size permitting).

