### 9.3 Variables

**Table 1. List of Study Variables**

Variable	Role	Data Source(s)	Operational Definition
Patient demographics	Baseline Sub-group identifier	Patient records	Age, ethnicity, weight, height, biomarker status, family history of breast cancer.
Clinical characteristics	Baseline Sub-group identifier	Patient records	Time since diagnosis, staging, node status, menopause status. ECOG/Karnofsky functional status, diagnosis for which palbociclib combination was prescribed, sites of metastases, de novo vs. recurrent disease.
Comorbid conditions	Baseline Sub-group identifier	Patient records	Comorbid conditions.
Early treatment history	Baseline Sub-group identifier	Patient records	Adjuvant treatments received since breast cancer diagnosis, time since end of adjuvant treatment, surgery/radiotherapy received.
Advanced treatment history	Baseline Sub-group identifier	Patient records	Treatments and supportive therapies received since metastatic/advanced HR+/HER2- diagnosis, duration of treatments, reasons for regimen changes.
Palbociclib combination treatment	Exposure Sub-group identifier	Patient records	Starting dose, duration of treatment, line of treatment, changes in dose, interruptions, cycle delays and discontinuations; where possible reasons for change in treatment.
Clinical outcomes	Outcomes	Patient records	Proportion progression free, ORR, TTP, PFS, patient death, 1-year and 2-year survival in all patients and within specific subgroups.

PFIZER CONFIDENTIAL

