## 9.8 Quality Control

To improve data quality the following actions will be undertaken:

- Provision of standardized instructions on study design, methodology and procedures.
  - Physicians will be contacted via email or telephone and an overview of the study will be provided (detailing study objectives, patient inclusion criteria, correct completion of eCRF and interview and any other logistical aspects of the study).
  - Follow-up with the physicians to ensure queries are resolved quickly.
- The electronic materials will be tested thoroughly to ensure that all questions appear correctly on screen, allow easy interpretation/completion and that all routing and logic checks are working correctly. As such, there should be no missing data (given the online nature of the study, the physician will have to complete a question before he/she is able to move on the next) however, ‘don’t know or unknown’ will be valid responses.
- To improve and secure data quality, automatic data checks upon data entry will be done within the eCRF. In the eCRF, plausible ranges of values for numeric data entries as well as logical data entries and listings will be provided for each entry field. Based on this, checks on completeness and plausibility will be performed upon data entry in the eCRF. All corrections will be visible from the systems audit trail.
- No regular monitoring or source data verification is planned in this study. However, in case of decreasing compliance (ie, of missing data, data discrepancies, protocol violations, etc.) a for-cause audit or risk-based monitoring visit will be performed.

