7 STATISTICAL METHODOLOGY AND STATISTICAL ANALYSES**7.1 STATISTICAL METHODS**

Analysis of the data will be performed by the Biostatistics and Statistical Programming team. All statistical analyses will be performed using STATA 13.0 Version or higher. The SAP will be finalized before database lock.

The following standard descriptive summaries will be presented:

[figure not shown]
[figure not shown]
Descriptive statistics for continuous data:

The continuous data will be summarized using the number of observations (n), arithmetic mean (mean), standard deviation (SD), median, minimum value (min), and maximum value (max).

The number of observations (n) will be presented with no decimal place, mean and median will be presented up to one decimal place from the original value, SD up to two decimal places from the original value and (min, max) as an original value.

Descriptive statistics for categorical data:

PFIZER CONFIDENTIAL

The categorical variables will be summarized using the frequency count (n) and percentage (%) for each possible value. The frequencies will be presented up to 0 decimal places, percentage up to 1 decimal place.

All the analysed variable will be presented by the line of treatment (1st line of treatment and 2nd and later line). If data are not available, a missing category will be presented. Statistical tests, if any, will be performed at 5% level of significance. The denominator for percentages will be based on the number of patients appropriate for the purpose of the analysis.

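### SAP Tables 6 and 6.1 report adjuvant therapy as a percentage of all subjects, although primary objective 2 concerns Stage 0-IIIa disease

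*SAP*

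**What the plan says.** The second primary objective (Protocol section 8, repeated in SAP 2.2) is limited by stage: "To summarize adjuvant therapies received for the treatment of early or locally advanced breast cancer (Stages 0-IIIa").

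The shell that serves it is listed in SAP section 8 as "Table 6 Early Breast Cancer Treatment History – All Subjects". The footnote under the shell in SAP Appendix 1 is: "Note 1: Percentages are based on the number of subjects in the Palbociclib group". The all subjects set in SAP 4.1 has no stage limit, and SAP 4.4 defines no subgroups.

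Other parts of the plan bear on who is counted:

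- SAP 7.1 sets a general rule: "The denominator for percentages will be based on the number of patients appropriate for the purpose of the analysis". It names no table and no stage.
- SAP 7.2 describes the Table 6 analysis thus: "Following early breast cancer diagnosis treatments received such as surgery, radiotherapy, neoadjuvant treatment, adjuvant chemotherapy, adjuvant endocrine therapy by patients will be summarized". It gives no denominator.
- Protocol Table 1 lists among the clinical characteristics "sites of metastases, de novo vs. recurrent disease". The Table 2 shell has rows for first diagnosis at IIIb, IIIc and IV.
- Protocol Table 1 defines early treatment history with no stage limit: "Adjuvant treatments received since breast cancer diagnosis".

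**The concern.** A woman whose disease was first found at Stage IV had no early-stage phase in which adjuvant therapy could be given. Under the Table 6 footnote she still counts in the denominator. The shell has a row for unknown but none for not applicable, so she cannot be told apart from an early-stage woman who went untreated.

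Followed as written, Table 6 prints the share of the whole cohort with a given therapy, not the share among women first diagnosed at Stage 0-IIIa. Where later-stage women have lower adjuvant use, the printed figure is below the Stage 0-IIIa rate. In Table 6.1 the two line-of-treatment columns can differ through stage mix alone. The study is purely descriptive, so these percentages are the result for a primary objective.

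The numerator is less clear. No SAP rule keeps later-stage women out of the treatment rows. The SAP 7.2 wording may be meant to, and so may the eCRF routing that Protocol 9.8 mentions ("all routing and logic checks are working correctly"). The CRF is not among the documents, and the Protocol Table 1 definition points the other way. This decides whether a reader could repair the figure afterwards.

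**Working it through.** **The plan's own figure.** The city rows of Protocol Table 2 sum to 20 + 10 + 40 + 20 + 10 + 10 + 20 + 20 = 150 records. This is the planned Table 6 denominator under the footnote. There is no sample-size calculation to reproduce.

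**Inputs.** From the documents: N = 150 and the approximate 7:3 split between first and later lines (Protocol 9.1), giving 105 and 45. Everything else is assumed, because the documents give no stage mix and no adjuvant rate: a true rate of 80% in Stage 0-IIIa women; *d*, the share first diagnosed beyond IIIa; and *r*, the rate of the same therapy in that share.

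**Table 6.** Printed percentage = 80% × (1 − *d*) + *r* × *d*.

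| *d* | *r* = 0 | *r* = 20% | *r* = 40% | *r* = 80% |
|---|---|---|---|---|
| 20% | 64% | 68% | 72% | 80% |
| 30% | 56% | 62% | 68% | 80% |
| 40% | 48% | 56% | 64% | 80% |
| 50% | 40% | 50% | 60% | 80% |

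Example: *d* = 30%, *r* = 0 gives 0.80 × 0.70 = 56%, which is 84 of 150. There is no distortion if *d* = 0 or *r* equals the Stage 0-IIIa rate.

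**Table 6.1.** Take each column's own total as its denominator, *d* = 40% in first line and 20% in later lines, and a true 80% in both columns. Stage 0-IIIa women then number 105 × 0.60 = 63 and 45 × 0.80 = 36.

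- *r* = 0: 0.80 × 0.60 = 48% against 0.80 × 0.80 = 64%.
- *r* = 40%: 48% + 0.40 × 40% = 64% against 64% + 0.40 × 20% = 72%.

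The gap of 16 or 8 points comes entirely from the assumed stage mix.

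**Can a reader rebuild the figure?** Take *d* = 30% (105 Stage 0-IIIa, 45 later) and 84 of 150 printed (56%).

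- No later-stage woman in the row: 84/105 = 80.0%. The 105 follows from Table 2 by subtracting the IIIb, IIIc and IV rows, even without a Stage 0 row.
- 7 later-stage women in the row: (84 − 7)/105 = 77/105 = 73.3%.
- 15 in the row: (84 − 15)/105 = 69/105 = 65.7%.

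If an unknown number up to 15 is counted, the rate lies anywhere from about 66% to 80%. No listed table crosses treatment with stage, so it cannot be pinned down.

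**Two smaller checks of shells against SAP 7.2.** The text promises initial stage from 0 to IV, but the Table 2 shell starts at Stage I. The text gives metastatic sites under metastatic disease, but the Table 3 footnote again divides by the whole group, and eligibility admits advanced disease that is not metastatic.

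**The case against.** The strongest reply is that the stage phrase in the objective qualifies the disease treated and does not name a denominator. The share of the whole cohort with prior adjuvant therapy is a fair baseline description, and the table is labelled as all subjects. The footnote is also generic: it stands under all 11 main shells, including rows it fits poorly, such as the type of induced menopause. SAP 7.1 already permits the narrower denominator. If later-stage women never enter the rows, the Stage 0-IIIa percentage can be rebuilt from Tables 2 and 6, and by line from Tables 2.1 and 6.1. Finally, every figure for the size of the effect is assumed, nothing in the documents supports a stage difference between lines, and no hypothesis depends on the table.

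Much of this stands. An all-subjects percentage is legitimate when labelled as such, the size is unknown, and recovery is possible under one reading. It does not remove the conflict. A programmer working from the shell has one explicit instruction, and it divides by everyone. The 7.1 sentence is too general to override it. Whether the figure can be rebuilt turns on a CRF rule the documents do not show. The restriction would also drop adjuvant treatment of IIIb and IIIc women from the main table, which is a reason to keep the all-subjects figure beside it.

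**Conclusion.** The point holds. The Table 6 population and footnote conflict with the stage limit in primary objective 2 and with the SAP 7.1 denominator rule, in the only visible table for that objective (redacted pages cannot be checked). That rests on the text alone.

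The size rests on assumptions. With a true 80% and 20% to 50% first diagnosed beyond IIIa, the shortfall is 16 to 40 points if none of the later-stage women had the therapy, 8 to 20 points if 40% did, and nil if their rate is equal. Whether later-stage women also enter the numerator is unsettled. This should be corrected before the tables are produced. It is not critical, because counts are still printed and no inference depends on them.

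**What to change.** - Present Tables 6 and 6.1 for patients first diagnosed at Stage 0-IIIa, in numerator and denominator, overall and within each line of treatment.
- Show that n and the number unknown or missing.
- Keep an all-subjects percentage only as a labelled extra, so that treatment of IIIb and IIIc women is not lost.
- Amend the footnote under these two tables to agree with SAP 7.1.
- Separately, add the Stage 0 row to Table 2 and base the Table 3 site rows on patients with metastatic disease, as SAP 7.2 describes.

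The work is a population line, some footnotes and one row. Initial stage is already to be summarised, so no new data item is needed. The price is precision. The 95% half-width around 80% is 1.96 × √(0.16/*n*): 6.4 points at *n* = 150, 7.2 at 120 (20% beyond IIIa) and 9.1 at 75 (50% beyond IIIa). The Table 3 site rows also lose the non-metastatic patients.
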